3.3.3 Control Group(s)

Does not apply in this extension study: all patients will continue the active treatment with Octanorm that they received in the main study SCGAM-01.

3.3.4 Target Parameters

The outcome measures in this study are consistent with previous studies of other IVIG or SCIG products and are also in compliance with the FDA Guidance for Industry.[22]

The QoL questionnaires are standardized, validated instruments that have been widely used in clinical studies, including PI.

3.3.5 Statistical Considerations

The FDA Guidance for Industry suggests that, based on historical data, a statistical demonstration of a serious infection rate per person-year less than 1.0 is adequate to provide substantial evidence of efficacy.^[22] Therefore, the 99% CI for this rate will be calculated at a descriptive level, without formal statistical testing (statistical tests may be performed on an ad hoc basis if this is considered appropriate).

Because a single patient may experience more than one SBI, the calculation of this confidence interval will take into account such intra-patient correlation, following a compound Poisson process model.

4 STUDY POPULATION

4.1 Population Base

Approximately 35 male or female patients suffering from PI will be eligible for inclusion to this clinical study.

4.1.1 Inclusion Criteria

Patients who meet all of the following criteria may be enrolled:

1. Completion of the main study SCGAM-01, with good tolerance of Octanorm (as determined by the investigator).
2. For adult patients: freely given written informed consent. For patients below the legal age of majority: freely given written informed consent from parents/legal guardians and written informed assent from the child/adolescent in accordance with local requirements.
3. For female patients of child-bearing potential, a negative result in a urine pregnancy test conducted at the Screening visit.
4. Willingness to comply with all aspects of the protocol, including blood sampling, for the duration of the study.

4.1.2 Exclusion Criteria

Patients who meet one (or more) of the following criteria are excluded from the study:

1. Subject being without **any** IgG treatment for period greater than 5 weeks between the last infusion of Octanorm in the SCGAM-01 study and the first infusion of Octanorm in the SCGAM-03 study.
2. Exposure to blood or any blood product or derivative, other than IgG used for regular PID treatment, within the 3 months before the first infusion in this study.
3. Planned pregnancy during the course of the study.

4.2 Prior and Concomitant Therapy

Details of any relevant concomitant medication (antibiotics, corticosteroids, premedication (if used), immunosuppressive or immunomodulatory drugs, blood or any blood product or derivative, IVIG other than Octanorm taken after the SCGAM-01 and before the SCGAM-03 study etc.) must be recorded in the electronic case report form (eCRF). Prior medication will be inferred from the study data of the main study SCGAM-01. For patients with an intermission between the studies SCGAM-01 and SCGAM-03 any additional medications taken in the intervening period are to be recorded.

4.2.1 Permitted Concomitant Therapy

Local anesthetics (EMLA or L-Max (lidocaine) cream, plaster, or similar product) to reduce pain associated with needle insertion are allowed. The use of such medication(s) must be recorded.

Routine premedication to alleviate potential tolerability problems is not allowed during the study. However, patients who experience (or experienced in the SCGAM-01 study) 2 consecutive TEAEs (that are likely to be prevented by premedication) are permitted to receive antipyretics, antihistamines, or antiemetic drugs. Non-steroidal anti-inflammatory drugs should be avoided.

4.2.2 Forbidden Concomitant Therapy

Treatment with any IMP (other than IgG products) within 3 months before first infusion of Octanorm in SCGAM-03 study, or during the study, is forbidden.

Administration of any blood- or plasma-derived product is forbidden during the study and should only be given for emergency reasons. Patients will be withdrawn from the study if IgG preparations other than Octanorm are administered during the study.

Premedication for the study SCIG infusions shall not be given, with the exception of permitted therapy as stated above (for patients with 2 consecutive TEAEs). Corticosteroids shall not be given as a pre-treatment to alleviate potential tolerability problems.

Treatment with oral or parenteral steroids for ≥ 30 days or when given intermittently or as bolus, at daily doses ≥ 0.15 mg/kg of prednisone or equivalent is forbidden.

Immunosuppressive and immunomodulatory drugs are also forbidden.

Octanorm must not be mixed with other medicinal products.

4.3 Withdrawal and Replacement of Patients

4.3.1 Premature Patient Withdrawal

Patients have the right to withdraw from the study at any time for any reason, without the need to justify. The responsible Investigator also has the right to withdraw patients from the study in case of AEs, poor compliance, or administrative reasons.

Reasons for premature patient withdrawal can be the following:

- Patient's decision: Should a patient decide to withdraw, the Investigator will make the best efforts to complete and report all information available at time of withdrawal. The Investigator will document the reason(s) for the patient's discontinuation.
- Withdrawal for safety reason: If the reason for removal of a patient from the study is an AE or an abnormal laboratory test result, this specific event or test will also be recorded. If a patient is withdrawn from the study because of an AE, the Investigator will make thorough efforts to clearly document the outcome.
- Administration of other immunoglobulin preparation: If for any reason a patient's therapy is changed to another IVIG or SCIG preparation within this study, the patient will be withdrawn from the study.
- Pregnancy: Pregnant patients may not be included in this extension study. A pregnancy test is mandatory for all females of child bearing potential at the Screening Visit, Week 12 Visit, and then every 24-weeks at scheduled study visits following the

Week 12 Visit until the Termination Visit. All female patients of childbearing potential are responsible for using effective contraception during their study participation. If a pregnancy occurs, treatment with the IMP must be stopped immediately and Octapharma's Central Drug Safety Unit must be informed.

If a patient is withdrawn, the Investigator will organize a Termination Visit. At this visit, all investigations including laboratory tests should be performed to allow the patient to be included in both safety and efficacy evaluations. This Termination Visit is identical to the follow-up visit of the last IgG administration.

4.3.2 Patient Replacement Policy

Patients withdrawn from the study for any reason will not be replaced.

4.4 Assignment of Patients to Treatment Groups

In the main study SCGAM-01, patients were recruited into four age strata: ≥ 2 years and < 5 years, ≥ 5 years and < 12 years, ≥ 12 years and < 16 years, and ≥ 16 and ≤ 75 years. In the present extension study, they will remain in the strata that they were in for analysis in the main study (irrespective of whether their age changed such as to imply a change of age stratum). Their maximum patient numbers will thus be the same as in the main study SCGAM-01. Each patient will be identified by this previously allocated number throughout the trial; no additional patient or randomization number will be used for this extension study.

All patients enrolled in this study will be treated with Octanorm.

Under no circumstances are patients who participate in this extension study and left it permitted to re-enroll.

4.5 Relevant Protocol Deviations

In the case of any major deviation from this study protocol, the Investigator and Octapharma will decide on the further participation of the patient in this study, after having discussed all relevant aspects.

A list of all included patients with all deviations from the intended study procedures and other criteria that may affect the validity of patient data for statistical analysis will be prepared after the clinical phase of the study is completed. The list will be discussed by a panel consisting of the clinical study manager, a medical expert of the Sponsor, the data manager and the study statistician. This panel will decide upon the inclusion of each patient in the analysis populations.

4.6 Subsequent Therapy

If a patient decides to withdraw from the study or is withdrawn by the Investigator, he/she may be switched back to the treatment that he/she received before participation in the main study or to another commercially available IVIG or SCIG.

5 INVESTIGATIONAL MEDICINAL PRODUCT(S)

5.1 Characterization of Investigational Product(s)

Name of Medicinal Product: Octanorm

Active ingredient of Octanorm: Human normal immunoglobulin

Table 1: Biochemical Characteristics of Octanorm

Parameter	
Total protein (of which ≥96% is human IgG)	150 – 180 mg per mL
Maltose	70 – 90 mg per mL
Octoxynol	≤5 µg per mL
TNBP	≤1 µg per mL
IgA	≤0.6 mg per mL
Polysorbate 80	10 – 60 µg per mL
pH	5.0 – 5.8
Osmolality	310 – 380 mOsmol/kg
Polymers + Aggregates	≤5% of the total chromatogram area
Monomers + Dimers	≥90% of the total chromatogram area
Fragments	≤5% of the total chromatogram area
Sodium	≤30 mmol/L

Each batch (lot) of Octanorm is prepared from at least 3,500 donations of human fresh frozen plasma. Effective viral reduction is obtained via a combination of 3 validated manufacturing steps: cold-ethanol fractionation, solvent/detergent treatment with TNBP and Octoxynol, and pH 4 treatment. The manufacture of Octanorm is based on the Octagam manufacturing process including an additional adsorption step onto commercially available and widely used chromatography column for the removal of coagulation factor XI. The process is identical up to the step of diafiltration. After this step the product solution is concentrated to a target concentration of 200 g/L. Polysorbate 80 and maltose are added during final formulation to final concentrations of 10-60 µg/mL and 70-90 mg/mL, respectively.

5.2 Packaging and Labeling

Octanorm is delivered in glass vials. Each Octanorm vial will be labeled in a booklet style as follows:

Master Label Canada

Investigational drug to be used only by a qualified investigator	
Octanorm 16.5% _____ mL	Lot #: _____
Protocol #: SCGAM-03	Exp. date: _____
Patient #:	
Solution for subcutaneous injection.	
1 mL contains: 165 mg protein of which $\geq 96\%$ is human normal immunoglobulin G.	
Store between 2-8°C, protected from light. Must not be frozen. Keep out of the reach and sight of children.	
Must be inspected visually for particulate matter and discoloration prior to administration. Solutions that are cloudy or have a deposit must not be used.	
To be warmed up to room or body temperature before use. After first opening, use immediately.	
Dosage: Please refer to the handling instruction provided.	
Sponsor: OCTAPHARMA Pharmazeutika Prod.Ges.m.b.H.; [name], Tel: [REDACTED]	

Master Label US

Caution: New Drug - Limited by Federal (or United States) Law to Investigational Use Octanorm Study: SCGAM-03	
Unit size: _____ mL	
1 mL contains: 165 mg protein of which $\geq 96\%$ is human normal immunoglobulin G.	
Solution for subcutaneous injection.	
To be stored at 36 °F to 46 °F, protected from light. Must not be frozen. Keep out of the reach and sight of children.	
Must be inspected visually for particulate matter and discoloration before administration. Solutions that are cloudy or have a deposit must not be used.	
To be warmed up to room or body temperature before use. After first opening, use immediately. Patient No.:	
Dosage: Please refer to the handling instruction provided. BB-IND number: 15617	
Sponsor: OCTAPHARMA Pharmazeutika Prod.Ges.m.b.H.; [name], Tel: [REDACTED]	

5.3 Conditions for Storage and Use

Octanorm must be stored and transported light-protected at 36 °F to 46 °F (2 °C to +8 °C) and must not be frozen.

Octanorm must not be used after its expiration date.

Authorized personnel at the individual study centers will ensure that the investigational product is stored in appropriate conditions in a secure refrigerator with restricted access.

5.4 Dose and Dosing Schedule

Octanorm is to be administered subcutaneously every week (± 2 days) or every second week (± 2 days) at double the weekly dose.

A minimum interval of 4 days must be observed between two single subcutaneous infusions.

If, during the study, the body weight changes by $>5\%$, the dose is to be adjusted to keep the dose constant on a 'mg per kg body weight' basis.

SCIG infusions will be administered at the study site or (self-administered) at home.

The infusion is to be given at the study site at Week 1, Week 12, and then every 12-weeks until the Final Infusion Visit.

Each of these study visit dates may deviate ± 2 weeks from the planned date. However, the deviations must not cumulate.

The patients' Octanorm dose can be individualized, if considered necessary by the investigator, by titrating upward or downward and should be based on the difference between each patient's measured serum total IgG trough levels while on Octanorm and each patient's *target* serum total IgG trough level as determined below. This individualization of dosing should take precedence over applying the corrected DCF.

5.5 Preparation and Method of Administration

Vials of Octanorm must be allowed to warm to room or body temperature before infusion. Thereafter, Octanorm should be infused subcutaneously using a syringe driver for precise infusion rates and standard infusion materials provided to the patients by the site. The correct amount of IgG taken from 12 or 48 mL vials of Octanorm will be infused with the aid of a syringe driver. The content of the vials will have to be transferred into the syringes suitable for the syringe driver selected. Remaining solution in a vial must be discharged.

Octanorm must not be mixed with other medicinal products. An aseptic technique must be used throughout the procedure.

Each vial must be examined visually for particulate matter and discoloration before administration. The solution should be clear or slightly opalescent. Solutions that are cloudy or have a deposit must not be used.

The patient or his/her relative or caregiver will be instructed at the clinic/doctor's office or at the infusion center in the use of the following:

- syringe driver,
- infusion techniques,
- keeping of a patient diary and
- measures to be taken in case of severe AEs.

Infusion sites:

The maximum number of infusion sites used simultaneously should not exceed 6.

Infusion sites should be at least 2 inches (approximately 5 cm) apart. The actual sites of infusion should be changed with each weekly (or bi-weekly) administration.

Infusion volume:

The volume can be up to 60 mL/per infusion site.

Infusion (flow) rate:

The maximum recommended flow rate is 60 mL/hr/site.

The maximum infusion rate for all sites combined is 240 mL/hr.

Increases in infusion rates and volumes may only be introduced if the previous 2 administrations were well tolerated by the patient.

The infusion volume and the flow rate should be increased gradually as tolerated to prevent infusion site reactions. See the parameters listed in Table 2.

Table 2: Infusion Volume and Flow Rate by Patient Weight

	Recommended Increase for Patients² <40 kg	Recommended Increase for Patients² ≥40 kg
Infusion volume mL/site per infusion cycle ¹	Approximately ≤5mL	Approximately ≤10 mL
Infusion flow rate mL/hour/site per infusion cycle ¹	Approximately ≤5mL	Approximately ≤10 mL

¹ weekly or biweekly depending on dosing regimen

² To account for non-precision flow rates of mechanical pumps, actual flow rate increases will be dependent on tubing size, number of infusion sites and needle gauge. Minor deviations in excess flow rates (<2 mL/site) would not be considered protocol deviations.

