
Safety Analysis Plan:
 
The safety analysis will comprise descriptive statistics, tabulations and listings of all TEAEs, safety laboratory results, vital signs and physical examination findings. All reported AEs will be coded according to MedDRA.
 
For this extension study, any AE is regarded as treatment-emergent if the patient migrated from the main to the extension study without being treated with another IgG product. If another product was used between the two studies, then an AE in the extension study is classified as treatment-emergent if onset or worsening is after start of the infusion of Octanorm at the screening visit. Only TEAEs are accounted for in the analysis.
 
For each TEAE, the time relative to the start of the infusion will be calculated and the TEAE will be classified as temporally associated if the onset is during the infusion or within 72 hours after the end of the infusion.
 
All reported events will be listed and tabulated in full detail, in particular the following key figures will be presented for each age group and for the study as a whole:
 
 • Total number of TEAEs reported. 	

Name of Sponsor/Company: OCTAPHARMA, Pharmazeutika Prod.Ges.m.b.H., [name]	
Name of Investigational Product: Octanorm	Protocol Identification Code: SCGAM-03
Name of Active Ingredient: Human Normal Immunoglobulin	Edition / Date of Protocol: October 04, 2018

• Number of temporally associated TEAEs.• Infusion rate at the onset of temporally associated TEAEs (frequencies and percentages).• Narratives will be prepared describing each death, other SAEs, and other significant AEs that are judged to be of special interest because of clinical importance. 
The QoL data will be presented descriptively by visit, along with the change from screening (defined as the first infusion).
	

FLOW CHART OF STUDY EVENTS

ASSESSMENTS	Screening – First visit (Week 65 of SCGAM-01)	Octanorm Treatment Visits					Termination (ET)
	---	---	Every 12 Wks ⁴ [every 24 wks]	---	Every 12 Wks ⁴ [every 24 wks]	---	---
WEEKS	1	12	24, 36, 48 [36]	60	72, 84, 94, 108, etc [84, 108, 132, etc]	Final Infusion Visit	One week after last infusion
Informed consent, In-/exclusion criteria ³	x						
Body weight ³	x	x	x	x	x	x	
Physical examination ³ , vital signs ¹	x	x	x	x	x	x	x
IgG trough levels ³	x	x	x	x	x	x	x

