3 INVESTIGATIONAL PLAN

3.1 Primary and Secondary Endpoints

3.1.1 Primary Endpoint

There is no single primary endpoint in this present extension study. The primary objective is to assess safety and tolerability in medium-to-long-term administration, and this will be assessed by means of the following variables:

- Occurrence of all treatment-emergent AEs (TEAEs) throughout the entire treatment period starting with the first infusion of IMP.
- Occurrence of temporally associated TEAEs.
- TEAEs by speed of infusion.
- Local injection-site reactions.
- Vital signs (blood pressure, pulse, body temperature, respiratory rate).
- Laboratory parameters (hematology, clinical chemistry and tests for viral safety).

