5.7.2 Assessment of Treatment Compliance

Patients will receive infusions at the study site and at home (administered at home by the patient or his/her relative or caregiver). Infusion details will be documented together with the batch number(s) in the eCRF.

Throughout the study, patients will be asked to document on a diary the date, batch (lot) numbers, number of vials, speed of infusion, injection site(s), occurrence of infections, TEAEs and local tissue reactions at injection sites, missed days from work/school/kindergarten/day care, inpatient hospital stays, and any changes in concomitant therapy between visits. The diary will be reviewed during the patient's infusion visit at the study site.

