### 11.1. Adverse Events

All reported AEs will be coded according to MedDRA.

An AE is defined as treatment-emergent, if first onset or worsening is during the *octanorm* treatment period. Only treatment-emergent AEs (TEAEs) are accounted for in the analysis.

For each TEAE, the time relative to the start of the infusion will be calculated and the TEAE will be classified as temporally associated if the onset is during the infusion or within 72 hours after the end of the infusion.

All reported events will be listed and tabulated in full detail, in particular the following key figures will be presented:

- Total number of TEAEs reported.
- Number of temporally associated TEAEs.
- Infusion rate at the onset of temporally associated TEAEs
- Narratives will be prepared describing each death, other SAEs, and other significant AEs that are judged to be of special interest because of clinical importance.

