### 11.2. Infusions with One or More Temporally Associated AEs

The number of infusions with at least one temporally associated adverse event (including AEs judged not to be related to *octanorm* by the investigator) over the total number of infusions will be calculated for each patient, and the ratio will be presented, including the associated upper one-sided 95% confidence limit. The calculation of this confidence interval will take into account the observed intra-patient correlation - this is necessary because each patient may experience more than one infusion with an associated AE; it can therefore not be assumed that the observed events are statistically independent.

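### The planned output for TEAEs by infusion speed has no denominator and no within-patient comparison, and speed itself depends on prior tolerance, so it cannot show how speed relates to adverse events

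*Protocol*

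**What the plan says.** - **Variable.** Protocol 3.1.1 lists "TEAEs by speed of infusion" among the variables that assess the primary objective. SAP 3.2.1 repeats it.
- **Output.** The one by-speed item in SAP 11.1 is "Infusion rate at the onset of temporally associated TEAEs". Protocol 9.2.3.1 has the same item, to be given by age group and for the whole study. The Study Outline adds that it is reported as frequencies and percentages. None of these names the infusions or patients at each speed, speed categories, a comparison within patients, or a caveat.
- **How speed is set.** Protocol 5.5: "Increases in infusion rates and volumes may only be introduced if the previous 2 administrations were well tolerated by the patient". It continues: "The infusion volume and the flow rate should be increased gradually as tolerated to prevent infusion site reactions". The ceiling is also given there: "The maximum recommended flow rate is 60 mL/hr/site". Good tolerance is not defined, no starting speed is stated, and no rule for slowing after an event is given.
- **Correlation within patients.** SAP 11.2 covers only the overall proportion of infusions with a temporally associated AE: "The calculation of this confidence interval will take into account the observed intra-patient correlation". Nothing similar is planned by speed.
- **Data.** Under Protocol 5.7.2 the diary records "speed of infusion, injection site(s), occurrence of infections, TEAEs and local tissue reactions at injection sites", and Protocol 8.1.1 requires the rate of each infusion to be verifiable from source records. SAP 9.4 restricts flow-rate summaries to centre visits.

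**The concern.** A reader of a safety table by speed wants to know whether a patient has more events when infused faster. The planned table describes events only. If most infusions run at the top speed, most events will sit there too, whatever speed does.

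The obvious repair, dividing by infusions at each speed, brings in a second problem. Because escalation requires two tolerated infusions, event-prone patients spend longer at slow speeds and are over-represented there. A pooled rate per infusion then compares different patients as well as different speeds.

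This matters because the variable serves the primary objective, SAP section 2 says planned analyses will go into regulatory submissions or manuscripts, and Protocol 1.1 itself notes that many adverse events of intravenous products are related to infusion rate. A real speed effect is therefore plausible and could be hidden or invented by the presentation.

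**Working it through.** The documents give no figure for TEAEs by speed, so there is none to reproduce.

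**Inputs from the documents.** About 35 patients (Protocol 9.1); up to 234 infusions each (Protocol 3.2; 4.5 × 52 = 234); ceiling 60 mL/hr/site (Protocol 5.5); local-reaction rates of 0.028 to 0.697 per infusion in earlier studies (Protocol 1.1), the only per-infusion event rates given.

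**Step 1: how strongly the rule selects.** The chance that two consecutive infusions are event-free is (1 − p)².

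- p = 0.028: 0.972² = 0.945
- p = 0.10: 0.90² = 0.81
- p = 0.30: 0.70² = 0.49
- p = 0.697: 0.303² = 0.092

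The rule sorts patients strongly only if some of them have high event rates.

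**Step 2: simulation.** 35 patients × 234 weekly infusions, 150 replicates. Assumptions not in the documents: start at 20 mL/hr/site; +10 after two event-free infusions, up to 60; mean event risk at the starting speed 0.028, 0.10 or 0.30; gamma spread between patients with coefficient of variation (CV) 0, 1.0 or 1.5; true risk ratio (RR) per +10 mL/hr/site of 1.0 (none) or 1.1 (harm); with or without a step down after an event. The pooled RR is the event rate at 60 divided by the rate at all slower speeds. The within-patient RR is Mantel-Haenszel stratified by patient. Under harm the true ratio of 60 to a slower speed lies between 1.1 (against 50) and 1.1⁴ = 1.46 (against 20).

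| Mean risk, CV | Step down | True effect | Rate, slower | Rate, 60 | Pooled RR | Within-patient RR | Infusions at 60 | Events at 60 |
|---|---|---|---|---|---|---|---|---|
| 0.028, 1.5 | no | harm | 0.0380 | 0.0401 | 1.05 | 1.29 | 96% | 97% |
| 0.10, 0 | no | harm | 0.1195 | 0.1464 | 1.23 | 1.23 | 96% | 97% |
| 0.10, 1.0 | no | harm | 0.1641 | 0.1432 | 0.87 | 1.26 | 96% | 95% |
| 0.30, 1.0 | no | harm | 0.7325 | 0.3074 | 0.42 | 1.23 | 83% | 67% |
| 0.028, 1.0 | yes | none | 0.0458 | 0.0252 | 0.55 | 1.07 | 91% | 84% |
| 0.10, 1.0 | yes | none | 0.1813 | 0.0671 | 0.37 | 1.05 | 73% | 50% |

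At 0.028, CV 1.0, no step down and no true effect, the pooled RR was 0.94 and the within-patient RR 0.99.

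**Step 3: both directions from one scenario.** Take the third row. The event-only table puts 95% of events at the top speed, which looks bad for fast infusion. The pooled rates give 0.1432 / 0.1641 = 0.87, which looks good for it. The within-patient ratio is 1.26, the modest harm that was built in.

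**Step 4: ranges with CV 1.0 to 1.5.**

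- No true effect: pooled 0.23 to 0.94 without step down and 0.13 to 0.55 with it; within-patient 0.99 to 1.07.
- True harm: pooled 0.28 to 1.16 and 0.15 to 0.58; within-patient about 1.23 to 1.29.

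With CV 0 the pooled ratio shows no material reversal: about 1.0 with no effect and 1.16 to 1.31 with harm. This confirms that differing tolerance drives the bias. The within-patient ratio is not perfect either: with step down, no effect and CV 0 it was 1.05 to 1.11, because speed then depends on the patient's own last event.

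**Step 5: data coverage.** On-site infusions fall at Week 1, every 12 weeks from Week 12 (19 visits up to Week 228) and at the final infusion: 1 + 19 + 1 = 21 of 234, or 9%. Centre-visit summaries alone would leave most infusions out of any denominator.

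**The case against.** The strongest reply is that the criticised analysis is not in the plan. Speed at event onset is a description of events; a pooled rate by speed is not specified, and table shells are deferred (SAP section 14). That stands. A reader might infer from the escalation rule that the plan makes faster infusion look safer, or that fast infusions come mainly from tolerant patients. The documents support neither. Without step down and with differing tolerance, 81 to 96% of simulated infusions and 55 to 97% of events fell at the top speed, so an event count could make fast infusion look worse. Selection then shows mainly as intolerant patients being over-represented among the slow infusions.

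The size is also open to challenge. Protocol 4.1.1 requires good tolerance in SCGAM-01, which may narrow the spread. The simulated rule blocks escalation after any event, whereas temporally associated TEAEs include unrelated ones within 72 hours that need not count as poor tolerance, so the simulation may overstate selection. This limits the figures but does not remove the problem. Protocol 4.2.1 foresees patients with two consecutive TEAEs, including in SCGAM-01, and SAP section 6 plans about 10 Canadian patients who were never in SCGAM-01.

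Finally, Protocol 9.2 makes all results descriptive. That rules out a need for a formal test, but not for a denominator or a comparison of like with like.

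**Conclusion.** The concern holds in conditional form. Followed exactly, the plan cannot show how speed relates to adverse events, although this is a primary-objective variable. The planned event-only table can mislead either way. Pooled rates per infusion, if derived from it, are confounded by tolerance and tend to understate harm when patients differ in tolerance.

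The size rests on event rate, spread in tolerance and any slowing after an event, none of which the documents give. Without slowing, it is small at about 3% per infusion with CV 1.0, larger but without reversal at CV 1.5 (1.05 against 1.29), and it can reverse the sign at 10% or more. With slowing, which the protocol neither states nor excludes, the pooled ratio fell well below 1 even at about 3% with no true effect. These figures show mechanism and plausible range; they do not predict this study's result. This is a worthwhile, inexpensive improvement to a descriptive analysis.

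**What to change.** Amend SAP 11.1 as follows.

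1. Define speed categories and report infusions and patients in each as denominators. Use home infusions from the diary and source records as well as centre visits. State which speed is assigned to an infusion, since a temporally associated event can start up to 72 hours after it has ended, and check that home records allow a speed per site.
2. Add a within-patient comparison, by speed, of infusions with and without a temporally associated TEAE: patient-stratified Mantel-Haenszel, conditional logistic regression, or a mixed model that separates within-patient from between-patient speed. Adjust where data allow for time on treatment and volume per site. Report the estimate descriptively with a CI, and do the same for local reactions.
3. Label the pooled table as not a comparison of speeds, because Protocol 5.5 makes speed depend on prior tolerance.

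A random intercept plus entry speed alone is a weaker choice. In a separate simulation (35 patients, 64 prior and 104 analysed infusions, 8% risk at 30 mL/hr/site for the median patient) it estimated a true odds ratio of 1.2 per 10 mL/hr/site as 1.09 to 1.23, depending on scenario.

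The cost is SAP wording, one extra analysis, use of home-infusion speeds, and a wide CI if events are few. No new data item is needed if the diary speeds are usable, and the escalation rule is not touched.
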